3.7 CLINICAL ENDPOINTS

The Composite Unified Huntington's Disease Rating Scale (cUHDRS) ([Schobel, et al., 2017](#)) and its individual components will be analyzed. The cUHDRS is defined as a combination of the following first four individual assessments:

- **Total Functional Capacity**

The Total Functional Capacity (TFC) represents the Investigator's assessment of the patient's capacity to perform a wide range of activities of daily living including working, chores, managing finances, eating, dressing and bathing. It is based on a brief interview with the patient and the study companion. Individual item scores range from 0 to 3 (by 1), total score ranges from 0 to 13 and higher scores represent better functioning. The total score is the sum of the individual item scores.

The scale is considered completed if there are no missing values. There will be no imputation for missing values. The total score will be derived only if each of the individual item scores is not missing.

- **Total Motor Scale**

The Total Motor Scale (TMS) is the sum of the individual motor ratings obtained during administration of the motor assessment portion of the UHDRS. Individual item scores range from 0 to 4 (by 1), total score range from 0 to 124 and higher scores represent more severe impairment.

For each of the scores (total or domains) if any of items is missing then there will be no imputation for missing data and the score will not be computed.

In addition to TMS, the 'maximal chorea in upper limb' item as well the maximal chorea (from TMS) will also be considered. The maximal chorea score is the sum of the seven maximal chorea items

- **Symbol Digit Modalities Test**

The Symbol Digit Modalities Test (SDMT) is used to assess attention, visuoperceptual processing, working memory and psychomotor speed. It has been shown to have strong reliability and validity ([Smith, 1982](#)). The patient must pair abstract symbols with specific numbers according to a translation key. The test measures the number of items correctly paired (maximum of 110) in 90 seconds.

- **Stroop Word Reading Test**

The Stroop Word Reading Test (SWRT) is a measure of attention, processing and psychomotor speed. Patients are presented with a page of color names printed in black ink and are asked to read aloud as many words as possible within a given amount of time (typically within 45 seconds). The number of words read correctly is counted and higher scores indicate better cognitive performance.

Based on the aforementioned assessments, the following formula is used to derive the cUHDRS where TFC, TMS, SDMT and SWRT are the raw total scores of each assessment:

$$\text{cUHDRS} = \left(\frac{\text{TFC} - 8.8}{2.8} \right) - \left(\frac{\text{TMS} - 34.4}{17.4} \right) + \left(\frac{\text{SDMT} - 25.2}{12.4} \right) + \left(\frac{\text{SWRT} - 58}{21.2} \right) + 10.0$$

The cUHDRS will be derived only if each of the individual components is not missing. No imputation for missing values will be conducted. The minimum possible score is -3.06. The maximum is not defined.

Descriptive statistics will be provided for all available data.

Due to the limited number of patients reaching the 9-months visit, the statistical modelling will be performed including the data up to 5 months.

Analysis of longitudinal change from baseline over time: The MMRM will be performed for the cUHDRS and its four components respectively. The fixed effects in the model will include the corresponding endpoint at baseline, visit, treatment, treatment by visit interaction, baseline age, baseline CAG repeat length, CAP score and region. Visit will be fitted as a repeated variable within a patient. An unstructured (UN) variance-covariance structure will be applied to model the within-patients' errors; if the model fails to converge, the following variance-covariance structures will be tested as alternatives in the pre-specified order: TOEPH, ANTE[1] and CSH. (See [Appendix 3](#) for technical details)

Least squares means estimates based on the MMRM model, at each time-point, along with corresponding standard error, 95% CI and *p*-value will be presented for each regimen as well as for the comparison of each active arm against placebo.

Model-based analyses for the association between the clinical endpoints and the CSF biomarkers: In order to model the relationship between a continuous response variable (e.g. the change in cUHDRS from baseline at 5 months) and a main predictor (e.g., baseline value of mHTT), a LRM will be used. The model will include treatment and treatment by main predictor interaction terms as independent variables. Age, CAG repeat length, CAP scores and region will be included for covariate adjustment.

3.8 MRI ANALYSES

A 3D T1-weighted structural MRI scan will be used to quantitate whole brain, caudate and intraventricular volumes. The only absolute measures are baseline volumes, while boundary shift integral (BSI) are used to assess changes in volumes over time. Three boundary shift integrals will be considered: K-means ventricular boundary shift integral (VBSI), K-means CBSI and K-means brain boundary shift integral (KNBBSI). To be noticed is that BSI values represent already a measure of change from baseline.

Only data with a QC flag equals to 'Pass' will be used in the analysis.

Descriptive tables and plots will be performed. The relationship between the MRI at baseline and CSF mHTT at baseline will be performed using the methods as described in Section 3.4.

In addition, the analysis of covariance (ANCOVA) will be performed to compare the percentage change of BSI at 3 months between the treatment groups. The model will include baseline age, CAG repeat length, baseline CAP score and treatment as covariate. The estimated treatment difference at 3 months and corresponding 95% CIs will be presented.

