4.7 BIOMARKER ANALYSES

For statistical modelling, raw concentration values of fluid biomarkers in their respective units will be log-transformed.

Change from Baseline in CSF mHTT Protein Level

The same MMRM model as for efficacy endpoints (see Section 4.4) will be used to model the change from baseline in mHTT (after log-transformation of mHTT). Results from the model will be back-transformed, in order to present model-based percent change in geometric means.

Due to data availability, the analyses of CSF mHTT protein level might not be completed by the time of the CSR writing so results of this analysis may be reported in an addendum to the CSR.

Annualised Percentage Change from Baseline in Whole and Regional Brain (Caudate, and Ventricular) Volume Measured by BSI, as Determined by Structural MRI

The same MMRM model as for efficacy endpoints (see Section 4.4), but without adjusting for baseline volume (as this is already taken into account by considering the percent change from baseline), will be used to model the annualized percent change from baseline in BSI, which means that the measured percent change from baseline to the analysis timepoint will be converted to reflect percent change from baseline normalized for the duration between baseline assessment and post-baseline assessment in years.

Change from Baseline in CSF NfL Protein Level

The same MMRM model as for efficacy endpoints (see Section 4.4) will be used to model the change from baseline in NfL (after log-transformation of NfL). Results from the model will be back-transformed, in order to present model-based percent change in geometric means.

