UHDRS	Y	Y	Y	Y	Y	all available	BSL 1 month, 5 months	Yes
BSI*	Y	Y		Y*	Y‡	all available	3 months	No**
BSL MRI Volume		Y	Y			all available	Screening	No
PK	Y	Y	Y			all available		No
ADA		Y	Y			all available		No

ADA= anti-drug antibody; BSI= Boundary Shift Integral; BSL=Baseline; CSF= cerebrospinal fluid; MRI= magnetic resonance imaging; MMRM= mixed-model repeated measures; mHTT= mutant huntingtin (protein); NFL= neurofilament light chain (protein); PK= pharmacokinetic; UHDRS= Unified Huntington's Disease Rating Scale; Y= Yes.

Absolute=measured data at a given time point.

Change (%Change)= change from baseline from a given post-baseline measurement (expressed as a percentage)

*BSI is already a measure of change in volume (thus the change is not derived as for the other variables)

‡ %-Change for BSI is derived as $\left(\frac{BSI}{baseline\ volume}\right) \cdot 100$

** ANCOVA will be applied to compare the percentage of change of BSI at 3 months between the treatment groups.

Table 2 Overview of Planned Outputs to Describe the Association Between Selected Pairs of Parameters

Paired Variables	Data Type				Time points**	Additional covariates in statistical models
	X-variable		Y-variable			
	Absolute	Change	Absolute	Change		
X=mHTT, Y= CSF Biomarkers (NFL, YKL-40 Tau Total Protein)	Y		Y		X and Y=BSL	BSL Age, CAG, CAP
	Y			Y	X=BSL, Y=3M, 5M, 7M	BSL Age, CAG, CAP BSL CSF BM
		Y		Y	X and Y=3M, 5M, 7M	BSL Age, CAG, CAP BSL CSF BM, BSL mHTT
X= CSF Biomarkers (mHTT, NFL, YKL-40 Tau, and CSF total protein) Y=Clinical endpoints (cUHDRS, TFC, TMS, SDMT, and SWR)	Y		Y		X and Y=BSL	BSL Age, CAG, CAP, Region
	Y			Y	X=BSL, Y=5M	BSL Age, CAG, CAP, Region BSL ClinEP
		Y		Y	X=3M, 5M, Y=5M	BSL Age, CAG, CAP, Region BSL ClinEP, BSL CSF BM
X=CSF-Nfl, Y=Plasma-Nfl	Y		Y		X and Y=BSL	NA
		Y		Y	X and Y=3M,5M	NA
X=mHTT, Y=MRI	Y		Y		X and Y=BSL	BSL Age, CAG, CAP

BM=biomarker; BSL=baseline; ClinEP=clinical endpoints; Change = Change from baseline; CSF= cerebrospinal fluid; MRI= magnetic resonance imaging; mHTT= mutant huntingtin (protein); NA=not applicable; NFL= neurofilament light chain (protein).

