Appendix 2 Schedule of Assessments (cont.)

Change; PGI-S = Patient Global Impression, Severity; PK=pharmacokinetic; Q8W=every 8 weeks; RBR = Research Biosample Repository; SDMT=Symbol Digit Modalities Test; SFU = safety follow-up; SMDDS = Symptoms of Major Depressive Disorder Scale; SWR = Stroop Word Reading; TFC = Total Functional Capacity Scale; TMS = Total Motor Score; UHDRS=Unified Huntington's Disease Rating Scale.

Notes: All assessments should be performed at the scheduled visit, unless otherwise specified. On treatment days, all assessments should be performed prior to dosing, unless otherwise specified.

- ^a A maximum of one re-screening will be allowed within 8 weeks of the initial screening failure for patients who fail the initial screening (e.g., as a consequence of abnormal laboratory values or general medical status not meeting inclusion or exclusion criteria). If re-screening is required, CAG repeat length testing does not need to be repeated and the screening MRI and viral serology from the initial screening may be acceptable as part of the re-screening assessments, if performed within 12 weeks of the baseline visit.
- ^b Patients who complete the treatment period will return to the clinic for a treatment completion visit at Week 101 (i.e., the EoT visit). All patients who discontinue study treatment prematurely but do not withdraw consent for continued participation in the study will return to the clinic for study visits at Weeks 53 and 69 (if not already completed) and at Week 101 (i.e., the EoT for ETT visit) for collection of at least the data for the primary and secondary endpoints (see Sections 2.1.1, 2.1.2, and 2.2 of the Protocol v3). If the ETT visit falls within ± 30 days of either scheduled visits at Week 53 or Week 69, then only ETT will be considered. The ETT visit should be performed 28 days (± 3 days) after the last dose. Patients will also attend the scheduled EoT for ETT visit at Week 101 for limited assessments including the collection of the primary and secondary endpoints (see Sections 2.1.1, 2.1.2, and 2.2 of the Protocol v3). Study visits should be planned as per the study schedule, however under exceptional circumstances, time window of ± 3 days can be utilized.
- ^c Informed consent must be documented before any study-specific screening procedure is performed and may be obtained more than 28 days before initiation of study treatment.

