Appendix 2 Schedule of Assessments (cont.)

- ^{bb} After informed consent has been obtained but prior to initiation of study drug, only serious adverse events caused by a protocol-mandated intervention should be reported. After initiation of study drug, all adverse events will be reported until 5 months after the final dose of study drug. After this period, all deaths, regardless of cause, should be reported. In addition, the Sponsor should be notified if the investigator becomes aware of any serious adverse event that is believed to be related to prior study drug treatment.
- ^{cc} The DCL will be assessed at screening only (i.e., without the full TMS assessment). The TMS scale will be assessed (excluding the DCL) at all other timepoints.
- ^{dd} Excluding MRIs, which have a visit window of –14 days.

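### The Original Design Cohort ANCOVA of 3-month BSI change ignores the scan-to-scan interval, which can run from about 72 to 112 days (rarely to 161–168): a minor loss of precision, cheaply fixed

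*SAP*

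**What the plan says.** All of the following is in SAP Version 1 unless stated otherwise.

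- **Comparison.** Section 3.8: "the analysis of covariance (ANCOVA) will be performed to compare the percentage change of BSI at 3 months between the treatment groups".
- **Model terms.** Section 3.8: "The model will include baseline age, CAG repeat length, baseline CAP score and treatment as covariate". No term for time between scans appears.
- **Derived variable.** A note to Table 1 reads "Change for BSI is derived as" BSI over baseline volume, times 100. Nothing is divided by elapsed time.
- **Baseline scan.** The Table 1 row "BSL MRI Volume" gives Screening as its time point. Appendix 2 places screening at Day -28 to Day -2.
- **Re-screening.** Appendix 2, footnote a: "A maximum of one re-screening will be allowed within 8 weeks of the initial screening failure". With the limit counted back from the baseline visit, it adds: "the screening MRI and viral serology from the initial screening may be acceptable as part of the re-screening assessments, if performed within 12 weeks".
- **Follow-up scan.** Footnote q puts the Week 13 MRI before the lumbar puncture, preferably by 7 to 14 days. Footnote dd, on visit windows, reads: "Excluding MRIs, which have a visit window of –14 days".
- **Later cohort.** SAP Version 3, Section 4.7, uses annualised percent BSI change, "normalized for the duration between baseline assessment and post-baseline assessment in years".

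Section 3.6 of Version 1 also lists associations of changes in CSF mHTT and other CSF biomarkers with BSI at 3 months. Version 1 defines no MRI analysis window. Its study-day rule (Section 3.4) counts from randomisation or first dose, not from the baseline scan.

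**The concern.** BSI measures change since the baseline scan. In a progressive disease, a patient scanned over a longer interval shows more change at the same underlying rate. Section 3.8 treats every pair of scans as one 3-month change, so differences in screening logistics enter the outcome as if they were differences in atrophy or ventricular expansion.

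Two things are at stake. One is the precision of a comparison with about 36 patients per arm (108 patients, three arms). The other is the meaning of a figure labelled as 3 months, part of which precedes the first dose. In the BSI association analyses the predictor is a patient's CSF change. Randomisation does nothing to keep that unrelated to scan interval, so the interval could distort the slope as well as blur it.

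**Working it through.** The plan gives no interval, power or variance figure for this analysis, so there is none to reproduce. The check is date arithmetic followed by an order-of-magnitude calculation.

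**Interval limits**

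Interval = days from baseline scan to Day 1 + days from Day 1 to follow-up scan.

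- Week 13 is (13 − 1) × 7 = 84 days after Day 1. With the 14-day early window, the follow-up scan falls at 70 to 84 days. Under footnote q's preferred timing it falls at 70 to 77 days.
- The baseline scan is 2 to 28 days before Day 1, or up to 12 × 7 = 84 days before if reused.

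| Case | Shortest | Longest | Ratio |
|---|---|---|---|
| First screening | 2 + 70 = 72 | 28 + 84 = 112 | 1.56 |
| Reused scan, follow-up at the visit | – | 84 + 84 = 168 | 2.33 (to 72) |
| Reused scan, follow-up 7 days before | – | 84 + 77 = 161 | 2.24 (to 72) |

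Stacking the ±3-day visit window, or counting from a Day -1 baseline visit, moves these limits by at most 3 days (69 to 171).

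**What the limits mean for one patient**

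The plan gives no atrophy rate. At assumed constant rates of 1% to 10% per year, change = rate × days / 365.25:

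| Rate per year | 72 days | 112 days | 168 days |
|---|---|---|---|
| 1% | 0.20% | 0.31% | 0.46% |
| 2% | 0.39% | 0.61% | 0.92% |
| 4% | 0.79% | 1.23% | 1.84% |
| 10% | 1.97% | 3.07% | 4.60% |

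**Spread of the interval**

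A uniform spread over n whole days has variance (n² − 1)/12.

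- *No reused scans, uniform over both windows.* Variance = (27² − 1)/12 + (15² − 1)/12 = 60.7 + 18.7 = 79.3. SD is 8.9 days, mean 15 + 77 = 92 days, CV 9.7%. The SE of the arm difference in mean interval is 8.9 × √(2/36) = 2.1 days.
- *10% reused, 29 to 84 days old (assumed share).* Variance = 0.9 × 60.7 + 0.1 × 261.25 + 0.09 × (56.5 − 15)² + 18.7 = 254. SD is 15.9 days, mean 96.1 days, CV 16.6%, SE 3.8 days.
- *Footnote q followed, no reuse.* Follow-up is at 70 to 77 days. Its instruction to do the screening MRI as early as possible is read here as Day -28 to -15 (an assumption). Variance = 5.25 + 16.25 = 21.5. SD is 4.6 days, mean 95 days, CV about 5%, SE 1.1 days.

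**Effect on precision**

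If the between-patient SD of 3-month change is k times its mean, interval variation adds about (CV/k)² to the variance. No value of k is given, so two are shown.

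- k = 1: added variance is 0.097² = 0.9% without reuse and 0.166² = 2.8% with 10% reuse. The SE rises by about 0.5% and 1.4%.
- k = 0.5: added variance is 3.8% and 11%. The SE rises by about 1.9% and 5%.

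**The case against.** The case against giving this much weight is strong, and most of it stands.

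- **No bias.** A reader might infer that unequal intervals bias the treatment comparison. The documents do not support that. The screening scan's results must be available before enrolment, so its timing cannot depend on arm. The remaining 14 days of follow-up latitude fall under the blind. Chance imbalance at 36 per arm is part of ordinary sampling error and is already reflected in the confidence interval.
- **The upper limit is rare.** Reaching 168 days takes a screening failure, a successful re-screen, a reused scan at the 12-week limit, and a follow-up scan on the visit day instead of 7 to 14 days before. The number of reused scans is not given. If footnote q is followed, the spread is about half that of the uniform assumption.
- **Version 3 does not contradict Version 1.** The cohorts have separate plans, and the Original Design Cohort is kept out of the main analysis. Annualising suits Version 3's repeated-visit model; Version 1 compares one time point.
- **Annualising is not clearly the better primary analysis.** Time on study drug before the Week 13 scan is nearly constant, at 70 to 84 days. Dividing by the whole interval keeps 70/72 = 0.97 of it as on-drug time in a short-interval patient, but 84/168 = 0.50 in the extreme reused-scan patient. A drug effect would be diluted according to screening history.

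Two things are left. Elapsed time is a known source of variation that the model omits, although scan dates would supply it. And the no-bias argument does not extend to the BSI association models.

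**Conclusion.** The point holds as a minor one. Section 3.8 of SAP Version 1 compares raw percent BSI change without accounting for a scan interval that its own schedule lets vary from about 72 to 112 days, and up to about 161 to 168 days when an old screening MRI is reused. In calendar terms (30.4 days per month), the 3-month label can cover about 2.4 to 3.7 months for most patients and 5.5 months at the extreme.

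The cost to the randomised comparison is precision only. The SE rises by roughly 0.5% to 5% across the scenarios worked above, and by less if footnote q is followed. Those figures rest on assumed uniform timing, an assumed reuse share of 0 to 10%, and an assumed ratio of SD to mean change of 0.5 to 1. For the BSI associations the effect could be distortion as well as noise; its size cannot be derived from the documents.

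The introduction to Version 1 rules out formal hypothesis testing and makes all p-values descriptive, so no confirmatory conclusion depends on this.

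**What to change.** In Section 3.8 of SAP Version 1, define the scan interval as the number of days between the baseline MRI and the Week 13 MRI, and add it as a continuous covariate in the ANCOVA. Add the same term to the models in Section 3.6 that have BSI as the response. Report the interval's distribution by arm, with the number of reused screening scans, so that the 3-month label can be read correctly.

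Optionally, report annualised percent change as a supplementary result for comparison with SAP Version 3, Section 4.7: (BSI / baseline volume) × 100 × 365.25 / interval in days. State that it averages over time before the first dose.

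The cost is one derived variable from the scan dates and one degree of freedom. If all 108 patients contribute, the ANCOVA's residual degrees of freedom go from 108 − 6 = 102 to 101.

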3.9 DIGITAL ENDPOINTS

The statistical analyses of digital endpoints will be described in a dedicated SAP.

3.10 PHARMACOKINETIC AND PHARMACODYNAMIC ANALYSES

All patients in the PK population (Section 3.1.3), CSF and plasma concentrations of RO7234292 will be presented descriptively, including arithmetic and geometric means, median, range, SD, and coefficients of variation.

3.11 IMMUNOGENICITY ANALYSES

For patients under treatment, there is a potential for them to develop ADA over time. The serum sampling for ADA assessment data will be available for baseline and pre-dose at each time point post-baseline. The immunogenicity analysis population will be used for the analysis. Data will be presented in summary tables (proportions of baseline prevalence and incidence of ADA by treatment arm) and a listing of patients who tested positive for ADA.

The following definitions based on (Shankar, et al., 2014) as well as a Sponsor's definition for ADA with neutralizing potential will be used to describe patients' immunogenicity:

- ADA-Positive
 - Treatment induced: ADA developed de novo (seroconversion) following drug administration. Patients who have no pre-existing ADA or are missing ADA data before drug administration and who have at least one ADA-positive sample following drug administration.
 - Treatment boosted: Patients who have pre-existing ADA and have a ≥ 4 fold increase in ADA titer following drug administration compared to baseline measurement.
- ADA-Negative
 - ADA-negative all samples: Patients who have no pre-existing ADA (i.e. antibodies reactive with the drug that are present in patients before treatment) or are missing ADA data before drug administration and who have all negative

ADA results following drug administration, and treatment unaffected ADA-negative patients.

- Treatment unaffected ADA: Patients who had positive sample at baseline and post-baseline were either negative or positive but do not have a ≥ 4 fold increase in ADA titer following drug administration compared to baseline measurement.

- Transient ADA
 - Treatment-induced ADA detected only at one sampling time point during the treatment or follow-up observation period (excluding the last sampling time point).
- Persistent ADA
 - Treatment-induced ADA detected at 2 or more sampling time points during the treatment or follow-up observation period, or detected on last sampling time point.

Table 1 Overview of Planned Analysis for the Longitudinal Changes Over Time

Parameter	Output presentation		Data Type			Time-points for descriptive statistics	Time points for MMRM	MMRM
	Plot	Table	Absolute	Change	% Change			
mHTT	Y	Y	Y	Y	Y	all available	BSL 1 month to 7 months	Yes
CSF Biomarker (NFL, YKL-40, Tau, and CSF total protein)	Y	Y	Y	Y	Y	all available	BSL 1 month to 7 months	Yes
Plasma NFL	Y	Y	Y	Y	Y	all available	BSL 3 months, 5 months	Yes
UHDRS	Y	Y	Y	Y	Y	all available	BSL 1 month, 5 months	Yes
BSI*	Y	Y		Y*	Y‡	all available	3 months	No**
BSL MRI Volume		Y	Y			all available	Screening	No
PK	Y	Y	Y			all available		No
ADA		Y	Y			all available		No

ADA= anti-drug antibody; BSI= Boundary Shift Integral; BSL=Baseline; CSF= cerebrospinal fluid; MRI= magnetic resonance imaging; MMRM= mixed-model repeated measures; mHTT= mutant huntingtin (protein); NFL= neurofilament light chain (protein); PK= pharmacokinetic; UHDRS= Unified Huntington's Disease Rating Scale; Y= Yes.

Absolute=measured data at a given time point.

Change (%Change)= change from baseline from a given post-baseline measurement (expressed as a percentage)

*BSI is already a measure of change in volume (thus the change is not derived as for the other variables)

‡ %-Change for BSI is derived as $\left(\frac{BSI}{baseline\ volume}\right) \cdot 100$

** ANCOVA will be applied to compare the percentage of change of BSI at 3 months between the treatment groups.

Table 2 Overview of Planned Outputs to Describe the Association Between Selected Pairs of Parameters

Paired Variables	Data Type				Time points**	Additional covariates in statistical models
	X-variable		Y-variable			
	Absolute	Change	Absolute	Change		
X=mHTT, Y= CSF Biomarkers (NFL, YKL-40 Tau Total Protein)	Y		Y		X and Y=BSL	BSL Age, CAG, CAP
	Y			Y	X=BSL, Y=3M, 5M, 7M	BSL Age, CAG, CAP BSL CSF BM
		Y		Y	X and Y=3M, 5M, 7M	BSL Age, CAG, CAP BSL CSF BM, BSL mHTT
X= CSF Biomarkers (mHTT, NFL, YKL-40 Tau, and CSF total protein) Y=Clinical endpoints (cUHDRS, TFC, TMS, SDMT, and SWR)	Y		Y		X and Y=BSL	BSL Age, CAG, CAP, Region
	Y			Y	X=BSL, Y=5M	BSL Age, CAG, CAP, Region BSL ClinEP
		Y		Y	X=3M, 5M, Y=5M	BSL Age, CAG, CAP, Region BSL ClinEP, BSL CSF BM
X=CSF-Nfl, Y=Plasma-Nfl	Y		Y		X and Y=BSL	NA
		Y		Y	X and Y=3M,5M	NA
X=mHTT, Y=MRI	Y		Y		X and Y=BSL	BSL Age, CAG, CAP

BM=biomarker; BSL=baseline; ClinEP=clinical endpoints; Change = Change from baseline; CSF= cerebrospinal fluid; MRI= magnetic resonance imaging; mHTT= mutant huntingtin (protein); NA=not applicable; NFL= neurofilament light chain (protein).

